5.7.2 Exposure adjusted incidence rate and 95% confidence interval

It will be assumed that for each of n patients in a clinical trial the time t_j ($j=1, \dots, n$) to the first incidence of a certain event is observed, or if the event was not experienced, the time is censored at the end of the observation period. The sequence of first occurrences of an event will be modeled to follow approximately a Poisson process θ with constant intensity λ . The rate parameter λ will be estimated by $\hat{\lambda} = \frac{D}{T}$, where $T = \sum_{j=1}^n t_j$ and D is the number of patients with at least one event. Conditionally on T , an exact 95% confidence interval for a Poisson variable with parameter θT and observed value D can be obtained based on (Garwood, 1936), from which an exact 95% confidence interval for $\hat{\lambda} = \frac{D}{T}$ will be derived as follows (Sahai, 1993; Ulm, 1990):

Lower confidence limit $L = \frac{0.5c_{\alpha/2, 2D}}{T}$ for $D > 0$, 0 otherwise,

Upper confidence limit $U = \frac{0.5c_{1-\alpha/2, 2D+2}}{T}$

where $c_{\alpha, k}$ is the α^{th} quantile of the Chi-square distribution with k degrees of freedom.

The SAS procedure GENMOD will be used to fit a Poisson regression model with only treatment as factor, the log-link and natural logarithm of time as the offset variable. The incidence rate (and 95% confidence intervals) are obtained as the exponentiated estimates by treatment (e.g. obtained by statement LSMEANS with option EXP). The data set will include a patient level response variable indicating whether the patient experienced at least one event of a specific type (1=yes, 0=no) and a patient level time variable which is derived as follows:

- For patients who had at least one event of that type: time is calculated as (start day of the first event - date of first administration of study drug+1).
- For patients who did not have an event of that type: time at risk as defined in Section 2.4.1 will be used.

The time will be divided by 365.25 before taking the logarithm transformation as offset variable so that the estimated incidence rate corresponds to an annualized rate.

6 Reference

Cockcroft DW, Gault MJ (1976) Prediction of creatinine clearance from serum creatinine. *Nephron*; 16:31-41

Garwood F. (1936) Fiducial Limits for the Poisson Distribution. *Biometrika* 28, 437-442.

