In Study OMS112831 of sc ofatumumab, the most commonly reported adverse events (AEs) across the ofatumumab dose groups were injection-related reactions (52% for ofatumumab, 15% for placebo). Injection-related reactions occurred primarily post-first dose, diminished on subsequent dosing and were mostly mild/moderate in severity (97% of the events). There were no notable differences across treatment groups in the overall incidence of infection-related AEs, including urinary and respiratory tract infections. Few serious adverse events (SAEs) were reported. These were mainly systemic injection-related reactions (3 patients), all occurring on Day 1 and in the 60 mg ofatumumab dose groups. There were no cases of opportunistic infections reported during the study. For further details about ofatumumab, please refer to the Investigator Brochure (IB).

Two multinational Phase 3 studies of ofatumumab (COMB157G2301 and COMB157G2302) are ongoing to provide efficacy, safety and tolerability data for sc injection of ofatumumab 20 mg every 4 weeks compared to oral teriflunomide in patients with relapsing MS, targeting 900 patients to be randomized in each study. Japan has not joined the Phase 3 studies because teriflunomide is not approved for use in patients with MS in Japan. Therefore, this placebo-controlled COMB157G1301 study, using the same dosing regimen in the Phase 3 studies, was planned to support registration of ofatumumab for treatment of relapsing MS in Japan.

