2.8.1 Adverse events (AEs)

Treatment emergent adverse events (TEAE) is defined as any adverse event which start on or after the day of the first dose of study drug.

TEAEs will be reported if their onset days are no greater than “time at risk for AE”. Similarly, serious TEAEs will be reported if their onset days are no greater than “time at risk for SAE”.

TEAE will be coded by primary system organ class and preferred term according to the Medical Dictionary for Regulatory Activities (MedDRA). The MedDRA version used for reporting the study will be described in a footnote.

Incidence of TEAEs will be summarized (number and percentage of patients reporting any TEAE by primary SOC, preferred term, and treatment group. Serious TEAEs, drug related TEAEs, TEAEs leading to premature discontinuation from study drug, TEAE leading to study drug interruption, and most common TEAEs ($\geq 5\%$ in any of the treatment groups) will be presented in a similar format as adverse events. In addition, incidence of TEAEs will be summarized by SOC, preferred term, and maximum CTCAE grade. Missing CTCAE grade will not be imputed. The CTCAE version 5.0 will be used.

For Cut-off 1 analysis, odds ratios (investigational drug vs. control) with 95% confidence intervals will be presented along with the summary of any TEAEs and the summary of serious TEAEs. Details in calculations of odds ratios and their 95% confidence intervals are provided in Section 5.7.1. Incidence of any TEAEs will be plotted by SOC, along with the odds ratio (and corresponding 95% confidence interval) for TEAEs in each SOC. Odds ratios provide appropriate inferences for events that are likely to occur at certain times (e.g., injection related reactions) while no constant risk over time is expected.

If a patient reports more than one adverse event within the same primary SOC, the patient will be counted only once with the maximum CTCAE grade at the SOC level, where applicable.

All AEs will be presented in listings.

The following summaries will be repeated for Cut-off 2 and final analysis:

- Overall TEAE
- TEAE by CTCAE grade
- Serious TEAE
- Drug-related TEAE
- TEAE causing study drug discontinuation
- TEAE leading to study drug interruption
- Serious TEAE causing study drug discontinuation
- Most common TEAE
- Infections and infestations TEAE

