2.8.1.1 Adverse events of special interest / grouping of AEs

Incidence of adverse events of special interest as defined in the latest version of case retrieval sheet (eCRS) at the time of each cut-off will be summarized by risk name, level, and treatment group. For Cut-off 1 analysis, odds ratios and 95% confidence intervals presented. The exposure-adjusted incidence rate of TEAEs that fulfill the risk search terms as defined in eCRS will also be summarized by risk name, preferred term and treatment group. For Cut-off 1 analysis, incidence rate ratios and 95% confidence intervals presented. Similarly, separate summaries will be provided for serious TEAEs that fulfill the risk search terms as defined in eCRS. Additionally, incidence or any TEAEs that fulfill the search terms as defined in eCRS will also be summarized by risk name, level, and maximum CTCAE grade.

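### SAP 2.8.1.1 and 5.7.2 do not exempt injection reactions from the constant-rate exposure adjustment; if the eCRS lists them, equal first-dose risk would show as unequal rates at Cut-off 2

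*SAP*

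**What the plan says.** - **SAP 5.7.2.** The rate is the number of patients with at least one event divided by the summed time to first event or censoring. The model is that "The sequence of first occurrences of an event will be modeled to follow approximately a Poisson process", with constant intensity. A patient with an event contributes the days from first dose to that event, so a same-day reaction contributes 1 day. A patient without one contributes the full time at risk from SAP 2.4.1.
- **SAP 2.8.1.1.** "The exposure-adjusted incidence rate of TEAEs that fulfill the risk search terms as defined in eCRS will also be summarized", by treatment group, using the eCRS version current at each cut-off. No risk is exempted. On between-arm contrasts: "For Cut-off 1 analysis, incidence rate ratios and 95% confidence intervals presented".
- **SAP 2.8.1.** Odds ratios are described as suitable "for events that are likely to occur at certain times (e.g., injection related reactions) while no constant risk over time is expected".
- **Protocol 1.1**, on the earlier subcutaneous study: "Injection-related reactions occurred primarily post-first dose, diminished on subsequent dosing". The incidence there was 52% on ofatumumab and 15% on placebo.
- **SAP 2.1.1, 2.1.4 and Table 2-11.** For Cut-off 2 safety the clock starts at the first ofatumumab dose: Day 1 in the continuous arm, Week 24 in the placebo-switch arm. AE time at risk ends at the earlier of 100 days after the last dose and the date of Cut-off 2, a single date normally set by the last patient's Week 48 visit.

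**The concern.** An events-over-time rate is comparable between groups with different follow-up only if risk is roughly constant over that follow-up. For an event that happens at the first dose or not at all, later event-free time adds to the denominator and nothing to the numerator. The rate then reflects how long patients were watched.

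The SAP recognises this for injection reactions in 2.8.1, but does not carry it into 2.8.1.1 or 5.7.2. At Cut-off 2 the two arms differ by design in time since first ofatumumab dose. A reader comparing the two rates in a table could conclude that patients switching from placebo react more often than those who started on ofatumumab, when the risk was the same. SAP 1.1 says that this analysis also supports registration in Japan.

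**Working it through.** The documents give no figure for an exposure-adjusted rate, so there is none to reproduce.

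**Inputs**
- Arms of 40 and 20: 60 patients randomized 2:1 (SAP 1.1).
- Reaction risk p = 52% in both arms, for illustration. It comes from the earlier study at other regimens and is not a first-dose-day figure; the ratio hardly depends on it.
- Every reaction falls on the first-dose day (1 day contributed).
- Follow-up from first ofatumumab dose: the Extension lasts 24 to 48 weeks (SAP 1.1), so 48 to 72 weeks in the continuous arm and 24 to 48 in the switch arm. The accrual spread is not given, so a range is shown.

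**Formula** (SAP 5.7.2): rate = D / T, where D = n × p and T = [D × 1 + (n − D) × days of follow-up] / 365.25.

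**Cut-off 2, 48 v 24 weeks**
- Continuous: D = 20.8; T = (20.8 + 19.2 × 336) / 365.25 = 6472 / 365.25 = 17.72 years; rate 1.17 per year.
- Switch: D = 10.4; T = (10.4 + 9.6 × 168) / 365.25 = 1623 / 365.25 = 4.44 years; rate 2.34 per year.
- Ratio 1.17 / 2.34 = 0.50.

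| Weeks, continuous v switch | Rates per year | Ratio |
|---|---|---|
| 48 v 24 | 1.17 v 2.34 | 0.50 |
| 60 v 36 | 0.94 v 1.56 | 0.60 |
| 72 v 48 | 0.78 v 1.17 | 0.67 |

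The ratio is close to switch follow-up over continuous follow-up (24/48, 36/60, 48/72). At 48 v 24 weeks it stays between 0.50 and 0.503 for p from 5% to 70%.

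**If some reactions come later.** In a simulation of 400,000 patients per arm, with a 24-week risk of 15% or 52% and the later reactions at constant hazard, the ratios were:

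| Share at first dose | 48 v 24 weeks | Extra 0-24 weeks, spread evenly |
|---|---|---|
| 80% | 0.61-0.64 | 0.71-0.75 |
| 50% | 0.77-0.81 | 0.85-0.88 |
| 0% | about 1.0 | about 1.0 |

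**Precision.** With 20 of 40 and 10 of 20 reacting at 48 v 24 weeks, the exact Poisson 95% limits are 0.66-1.67 around 1.08 and 1.04-3.97 around 2.16. They overlap.

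**Cut-off 1.** Completers in both arms have about 24 weeks. With 52% v 15%:
- Ofatumumab: 20.8 / [(20.8 + 19.2 × 168) / 365.25] = 2.34 per year.
- Placebo: 3 / [(3 + 17 × 168) / 365.25] = 0.383 per year.
- Rate ratio 6.1; odds ratio (0.52 × 0.85) / (0.15 × 0.48) = 6.14; risk ratio 0.52 / 0.15 = 3.47.

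The rate ratio agrees with the odds ratio, the measure that SAP 2.8.1 prefers.

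**After the change.** With crude incidence, equal first-dose risk shows as 52% v 52%. With the rate limited to the first 24 weeks on ofatumumab in both arms, it is 2.34 v 2.34, ratio 1.00.

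**The case against.** **The eCRS is not in the documents.** The rate applies only to terms that the eCRS lists. SAP 2.8.1.1.1 takes injection reactions from dedicated CRF pages, prescribes proportions and time to onset, and mentions no exposure-adjusted rate. This stands. That they are the first sub-heading of the special-interest section makes inclusion likely, not certain.

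**The rate may not be produced at Cut-off 2.** The list in SAP 2.8.1 of summaries to be repeated does not name the special-interest tables, and time at risk has other uses. Against that, the sentence requiring the rate has no Cut-off 1 limit, the eCRS is taken at each cut-off, and SAP 2.4.1 ties time at risk to exposure-adjusted rates and defines it for Cut-off 2 and final. A Cut-off 2 rate is the more natural reading.

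**Unaffected outputs are already planned.** SAP 2.8.1.1.1 repeats proportions with site and systemic reactions at Cut-off 2. SAP 2.8.1.2 gives incidence by first onset period; its Day 1-90 column covers the same window after first ofatumumab dose in both arms. This is the strongest objection, and it limits the harm. It does not remove a rate row that would disagree with those outputs without explanation. Cumulative proportions are also an imperfect check if some reactions come later: in the simulation with 80% at first dose and 52% risk, they were 60.5% v 51.9% at 48 v 24 weeks.

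**Stronger readings that the documents do not support.** A reader might infer that the continuous-arm rate will be half. That needs every reaction at the first dose and every patient at exactly 48 or 24 weeks; protocol 1.1 says primarily, and Cut-off 2 is one date, so earlier-enrolled patients have longer follow-up. A reader might infer that the Cut-off 1 rate ratio is inflated because 6.1 exceeds 3.47; it matches the odds ratio over equal follow-up. A reader might count the missing Cut-off 2 odds ratio as a defect; it contrasts investigational drug with control, and by then both groups receive ofatumumab.

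**Conclusion.** The concern holds in a limited form. The plan applies a constant-intensity rate to all eCRS risk terms without exempting a class of event for which it says elsewhere that constant risk is not expected. At Cut-off 2, equal risk would show as a continuous-arm rate of about 0.50 to 0.67 of the switch-arm rate if all reactions fall at the first dose. With 80% at the first dose the range is about 0.61 to 0.75, and it moves towards 1 as more reactions come later.

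This rests on three assumptions: the eCRS lists injection reactions, the rate is produced at Cut-off 2, and reactions cluster at the first dose as in the earlier study. It concerns descriptive rates shown side by side. No Cut-off 2 rate ratio or test is specified, and efficacy conclusions are untouched. The point is minor, but worth settling because the analysis supports a registration.

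**What to change.** Add one sentence to SAP 2.8.1.1 and 5.7.2: at Cut-off 2 and final, exposure-adjusted rates are not produced for injection-reaction terms, or are limited to a common window after the first ofatumumab dose (for example the first 24 weeks).

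Refer instead to the per-injection and cumulative proportions in 2.8.1.1.1 and to the Day 1-90 column of 2.8.1.2. State that at Cut-off 2 the per-injection display is aligned to the first ofatumumab injection; the plan labels injections by visit week, which would set the switch arm's first ofatumumab injection (Week 24) beside a later one in the continuous arm. Keep 5.7.2 for risks spread over time, such as infections.

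The cost is a sentence and a few table rows, with no new data. The small downside is that one risk is missing from the rate table. If the eCRS does not list injection reactions, the sentence changes nothing.

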2.4 Treatments (study treatment, rescue medication, concomitant therapies, compliance)

2.4.1 Study treatment / compliance

Analyses detailed in this section will be performed for Cut-off 1 analysis, Cut-off 2 and final analysis.

For the core part and the extension part, duration of exposure to study drug is defined as (last dose date) – (first dose date) + 31 – sum[(j+1)-th injection date – j-th injection date - 31], where j and j+1 refer to consecutive injections with injection dates more than 31 days apart (as patients are scheduled to take the subcutaneous injections every 28+/- 3 days).

Duration of exposure to study drug of core part and extension part will be summarized by treatment with number and percentage of patients and by duration category (i.e., >= 1 week, >= 2 weeks, >= 3 weeks, >= 4 weeks, >= 8 weeks, >= 12 weeks, >= 24 weeks, >= 36 weeks, >= 48 weeks, >= 60 weeks, >= 72 weeks, until end of the study). The number of patient years of exposure is calculated as (the sum of the number of days of exposure for all

patients in the group)/365.25 and will be summarized for each treatment arm, and by stratification factor Japan vs non-Japan.

Time at risk is the censoring time used for estimating exposure adjusted incidence rate of SAEs or AEs in patients who did not experience the event of interest. For patients who have experienced the event of interest, the actual date of the SAE, or AE onset will be used. Time at risk corresponds to the time window used for adverse event reporting and can serve as a denominator to certain safety analyses (e.g. in exposure-adjusted incidence rates).

Table 2-10 includes definition of time at risk for AE and SAE for Cut-off 1 analysis. It will determine the “end date of the Core part” when all randomized patients completed their assessment during the Core part.

Table 2-10 Time at risk for AE and SAE: Cut-off 1 analysis

Category	For those who completed Week 24 visit	For those discontinued the study prior to Week 24 visit
Time at risk for AE	Number of days in the study from first date of study drug to Week 24 visit date	Number of days in the study from first date of study drug to the earlier date of the following: - Safety cut-off - “End date of the Core part”*
Time at risk for SAE		Number of days in the study from first date of study drug to “end date of the Core part”

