2.16 Interim analysis

No interim analysis will be conducted.

3 Sample size calculation

A total sample size of 60 patients, randomized 2:1 to ofatumumab and placebo, will provide more than **90% power** for a statistical test of superiority of ofatumumab compared with placebo at a one-sided alpha level 0.025. The power was calculated based on a negative binomial model under the assumption of 1.0 Gd-enhancing T1 lesions per scan for placebo and a 92% relative reduction with ofatumumab (i.e. 0.08 Gd-enhancing T1 lesions per scan for ofatumumab), and a dispersion parameter $\kappa = 4.5$ (as observed in the combined Phase 3 placebo-controlled studies of fingolimod, namely FREEDOMS and FREEDOMS II studies for the same parameter, data on file). The sample size allows for a dropout rate of 10%.

Sample size calculation was done in EAST 6, version 6.3, Cytel Inc.

3.1 Evaluation of consistency in the treatment effect on the primary variable across regions

As a secondary objective the effect of ofatumumab on Gd-enhancing T1 lesion compared with placebo will be estimated for individual regions (Japan and other countries). It is planned to include 30 patients from Japan out of 60 in total.

The randomization will be stratified by region (Japan or other countries), and by Gd-lesion status on the screening scan (0 Gd-enhancing T1 lesions or ≥ 1 Gd-enhancing T1 lesions). Under the protocol assumptions for placebo, it is expected that approximately 2/3 of the patients will be free of Gd-enhancing T1 lesions at baseline.

A simulation was performed to evaluate the consistency in efficacy on the primary variable across regions. Consistency is defined as a rate ratio < 1 in both Japan and other countries. For the simulation the following assumptions apply:

- The assumptions for the primary variable are the same for Japan and other countries and identical to those for the primary endpoint (i.e. 1 Gd-enhancing T1 lesion per scan, a rate-ratio of 0.08 between ofatumumab and placebo, dispersion 4.5)

- In addition, it was assumed that the study would include 30 patients from Japan and 30 from other countries, and that patients would be randomized 2:1 to ofatumumab or placebo group in each region.

The probability to observe a consistent treatment effect between Japan and other countries was estimated to be higher than 99% under these settings.

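### SAP 5.7.2 names two different 95% intervals for the same exposure-adjusted AE rate, and the GENMOD one gives no usable placebo rate or rate ratio when placebo has no events

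*SAP*

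**What the plan says.** SAP 5.7.2 models first occurrences as a Poisson process and estimates each rate as D/T, where D is the number of patients with at least one event and T is the summed time. It then gives two routes to an interval.

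- **Exact route.** It refers to "an exact 95% confidence interval for a Poisson variable with parameter" θT and writes out chi-square limits for D/T. The lower limit is set to 0 when D = 0, and the upper limit uses 2D+2 degrees of freedom, so a zero count is covered.
- **Model route.** The next paragraph says "The SAS procedure GENMOD will be used to fit a Poisson regression model with only treatment as factor", with a log link and log time as offset. It continues: "The incidence rate (and 95% confidence intervals) are obtained as the exponentiated estimates by treatment (e.g. obtained by statement LSMEANS with option EXP".

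The rates are used in SAP 2.8.1.1, for adverse events matching the eCRS risk search terms, by risk name and preferred term, with separate summaries for serious events. That section adds: "For Cut-off 1 analysis, incidence rate ratios and 95% confidence intervals presented". Section 5.7.2 writes no interval formula for that ratio.

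SAP 5.7.1, on odds ratios, uses a conditional exact interval and has three display clauses for zero or all-event cells. Section 5.7.2 has no such clause for the GENMOD output or the rate ratio.

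**The concern.** Both routes address the same quantity, the rate in each treatment group. Limits formed by exponentiating a log-scale estimate and its standard error are Wald limits, which differ from the exact ones when counts are small. Two programmers following the same section could produce different tables.

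The log-scale model also cannot represent a rate of zero. If the GENMOD sentence is followed, a risk term with no placebo event has no finite placebo estimate, and the ratio to ofatumumab cannot be used. At stake is the between-group comparison of special-interest events at Cut-off 1, the analysis meant to support registration in Japan. It would be missing in some of the sparsest rows.

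**Working it through.** SAP 5.7.2 states formulas but no numerical result, so there is no figure of its own to reproduce.

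**Inputs**
- Arm sizes: "A total sample size of 60 patients, randomized 2:1 to ofatumumab and placebo" (SAP Section 3) gives 40 and 20.
- Time at risk for a patient completing Week 24 (SAP 2.4.1, Table 2-10): "Number of days in the study from first date of study drug to Week 24 visit date", taken as 168 days.
- Placebo T = 20 × 168 / 365.25 = 9.20 patient-years; ofatumumab T = 40 × 168 / 365.25 = 18.40. Simplification: time is not cut at the event for patients who have one.

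**Formulas**
- Exact: lower = 0.5·χ²(0.025; 2D)/T, or 0 if D = 0; upper = 0.5·χ²(0.975; 2D+2)/T.
- Model: a treatment-only Poisson log-link fit gives the rate D/T with log-scale standard error 1/√D, so the limits are (D/T)·exp(±1.96/√D).

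**Placebo, T = 9.20, rates per patient-year**

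| D | Exact | Model |
|---|---|---|
| 0 | 0 to 0.401 | not estimable |
| 1 | 0.003 to 0.606 | 0.015 to 0.772 |
| 2 | 0.026 to 0.785 | 0.054 to 0.869 |
| 5 | 0.176 to 1.268 | 0.226 to 1.306 |
| 10 | 0.521 to 1.999 | 0.585 to 2.020 |

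Written out for D = 1: the exact lower limit is 0.5 × 0.0506 / 9.20 = 0.003 and the upper is 0.5 × 11.143 / 9.20 = 0.606. The model gives 0.1087 × exp(±1.96) = 0.015 and 0.772. Its lower limit is 5.6 times the exact one and its upper limit 27% higher. These two factors do not depend on T. With 18 placebo patients (the planned 10% dropout removed entirely, T = 8.28), the exact upper limit at D = 0 is 0.446.

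**Zero placebo events: 4 on ofatumumab, 0 on placebo (illustration)**

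The treatment-only model was fitted in statsmodels, not SAS.
- The placebo log-rate was −17.6, −27.6 and −31.6 at iteration limits of 15, 25 and 50, so it does not settle.
- The placebo interval was 0 to infinity, and the rate ratio moved from about 10⁷ to about 10¹³.
- The ofatumumab rate was stable at 4/18.40 = 0.217, with model interval 0.082 to 0.579 (exact 0.059 to 0.557).

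A conditional exact interval for the ratio exists. Given 4 events in total, the ofatumumab count is binomial with p = RR·T₁/(RR·T₁ + T₀). The lower 95% limit for 4 of 4 is p = 0.025^(1/4) = 0.398, so RR = (0.398/0.602) × (9.20/18.40) = 0.33. The upper limit is infinite.

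**How often this would arise**

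The incidences are assumptions; the documents give none for the risk terms. P(0 of 20) = (1 − p)²⁰.

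| Assumed placebo incidence | Chance of zero events in 20 |
|---|---|
| 1% | 82% |
| 3% | 54% |
| 5% | 36% |
| 10% | 12% |
| 15% | 4% |

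The 15% row matches the placebo frequency of injection-related reactions in the earlier subcutaneous Phase 2 study (Protocol 1.1).

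**The case against.** The best defence is that the harm is limited, and much of it stands.

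- **Zero counts in 5.7.2.** A reader might infer that the section ignores them altogether. It does not: the exact formula handles D = 0. The gap concerns only the GENMOD output and the rate ratio.
- **Events seen only on ofatumumab.** A reader might infer that such an event would have no interval at all. The fit above shows that the ofatumumab rate keeps one; the placebo rate and the ratio fail.
- **Missed imbalances.** A reader might infer that such an imbalance would go unnoticed. SAP 2.8.1.1 also asks for incidence with odds ratios at Cut-off 1, and 5.7.1 gives those a conditional exact interval and a clause that sorts events absent on control to the top. The imbalance would still be flagged.
- **Scope.** The exposure-adjusted rates are called for only in SAP 2.8.1.1. The general tables in SAP 2.8.1 use counts and percentages, with odds ratios for any and for serious events, so adverse event reporting as a whole is not affected.
- **Frequency.** That zero counts will be common is not established by the documents. It is likely for terms at about 5% or below and unlikely for frequent reactions.
- **Wording.** The SAP never says Wald, and LSMEANS is offered as an example. The label is inferred from exponentiating model estimates.

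It might also be argued that GENMOD is meant only for the ratio. The text does not allow that reading, since it takes the rates and their intervals by treatment group from the model. None of these points says which interval is reported or supplies the ratio that SAP 2.8.1.1 requires.

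**Conclusion.** The point holds for the exposure-adjusted rates of eCRS risk-term events. SAP 5.7.2 gives two incompatible instructions for one interval. They differ materially at one or two events and little by ten. At zero placebo events the model route fails for the placebo rate and for the Cut-off 1 rate ratio.

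The sizes assume 20 placebo patients with full 24-week follow-up. The chance of a zero count depends wholly on the assumed incidence, from 82% at 1% to 4% at 15%. No test or decision rule uses these intervals, and the primary endpoint and its power are untouched. This is a correction to a descriptive safety summary, worth making because the plan as written leaves the reported interval open and a required ratio without a workable method.

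**What to change.** In SAP 5.7.2:

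1. State that the exact chi-square interval already written there is the one reported for each treatment group's rate, with D/T as the estimate, and delete the sentence that takes those intervals from GENMOD.
2. For the Cut-off 1 rate ratio, specify a conditional exact (binomial) interval and write out its formula.
3. Add a display rule modelled on 5.7.1: when one arm has no events, show the ratio with its one finite bound (for 4 against 0 events, 0.33 to infinity); when neither arm has events, show it as not estimable.

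The cost is SAP wording plus a small programming change for the ratio interval, whose formula is not yet in the SAP. No data collection changes.
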